8 STATISTICS AND DATA ANALYSIS

8.1 Sample size calculation

The primary outcome of this trial is the patient enablement instrument (PEI) at 2 week follow up. As patients are asked to retrospectively rate the level of enablement, at the 2-week follow up, as a result of their visit to the Staffordshire Musculoskeletal Interface Service we only have a score at a single time point (and not a change score) for each group of patients in Phase 1 and Phase 3. The Patient Enablement Instrument consists of six items graded on three-point scales. It is scored between 0 and 12 and a high score represents more enablement. The sample size was generated based on that required for an independent groups two-sample t-test with a two tailed 5% significance level at 80% power. As no Minimally Clinically Important Difference (MCID) relevant to the specific context could be found for the PEI, the study is powered to find a 0.40 effect size – representative of a small to medium effect. The expected SD for the population is 3.86 thus, the implied MCID between the groups would be a score of 1.55 scale points. Accordingly, the required sample is 100 in each arm. If we account for 50% dropout and missingness, the target recruitment is 200 in both phases 1 and 3.

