The primary outcome of this trial is the patient enablement instrument (PEI)¹ at 2 week follow up. As patients are asked to retrospectively rate the level of enablement, at the 2-week follow up, as a result of their visit to the Staffordshire Musculoskeletal Interface Service we only have a score at a single time point (and not a change score) for each group of patients in Phase 1 and Phase 3. The Patient Enablement Instrument consists of six items graded on three-point scales. It is scored between 0 and 12 and a high score represents more enablement. The sample size was generated based on that required for an independent groups two-sample t-test with a two tailed 5% significance level at 80% power. As no Minimally Clinically Important Difference (MCID) relevant to the specific context could be found for the PEI, the study is powered to find a 0.40 effect size – representative of a small to medium effect.² The expected SD for the population is 3.86¹ (taken from Howie et al. 1998) thus, the implied MCID between the groups would be a score of 1.55 scale points. Accordingly, the required sample is 100 in each arm. If we account for 20% dropout and missingness, the target recruitment is 120 in both phases 1 and 3.

6. Participant characteristics

Baseline characteristics for participants will be displayed in relation to the two groups of participants, i.e., those who are enrolled Phase 1 and those who are enrolled in Phase 3. Given the fact that patient groups are not randomly allocated hypothesis testing will be done comparing the groups at baseline for comparability.

See Tables in section 9 for details of which variables will be collected and how they will be reported.

7. Methods of analysis

Descriptive statistics:

For all outcomes, numerical variables will be summarised as either mean (SD) or median (IQR) depending on the skew of the distribution of the variable in question. Categorical variables will be described as frequencies and percentages.

Primary outcome measure:

A two-tailed independent sample t-test will be conducted to compare the mean PEI score in Phase 1 with that in Phase 3. An effect size, Cohen's Delta, and 95% confidence intervals will be reported for the mean difference between scores. A p-value will be reported with a significance level rate of < 5% leading to a rejection of the null hypothesis of no difference between the two groups.

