Model residuals will be checked for normality, if deviation is found appropriate transformations will be made to the PEI score. Exploration of patterns of missingness will be undertaken to look for potential associates with baseline. Under the assumption of Missing at Random (MAR) missing data on the primary outcome measure will be imputed via the multiple imputation by chained equation (MICE) method³. Sensitivity analysis will be conducted to assess impact of the MAR assumption. Analyses will be done with missing values both ± 1.55 scale points (the implied MCID) on the PEI – to model the potential effect of Missing Not at Random Bias (truncated between 0 – 12).

Secondary outcome measures:

Secondary outcome measures will be analysed via t-test. Effect sizes and 95% confidence intervals will be reported for all measures. P-values will be reported and a <5% rejection criterion will be utilised. No sensitivity analyses will be undertaken and no corrections for multiplicity will be made for the secondary outcomes.

Feasibility outcomes:

Only descriptive statistics for the feasibility outcomes will be reported. These will be counts and percentages with an appropriate denominator for each measure.

Technical details:

It is envisioned that R (current version 3.5.1) will be used for all analyses. The primary outcome will be analysed by the two study statisticians, unblinded. The statistical analyses and associated datasets will be kept in the appropriate section of the trial master file on the internal secure network.

8. References

1. Howie JG, Heaney DJ, Maxwell M, Walker JJ. A comparison of a patient enablement instrument (PEI) against two established satisfaction scales as an outcome measure of

primary care consultations. *Fam Pract.* 1998;15(2):165-171.

2. Cohen J. A Power Primer. *Psychol Bull.* 1992;112(1):155-159.

9. Tables/Figures

Feasibility/process outcomes

Potential participants	Phase 1 (before)	Phase 3 (after)	Total
Number of patients invited to take part			
Actual participants:			
Study consent & Completed baseline survey			
Consultation audio recording			
Clinician completed case report form in clinic			
Patient received clinic summary action plan			
Accessed goal setting module			
Patient completed 2-week FU survey			
Patient needed a reminder email for 2-week FU survey			
Patient completed 3-month FU survey			

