Patient enablement index – Mean (SD) [score range is 0 to 12: higher scores = better empowerment] This items asks – “As a result of your visit to the clinic, do you feel you are:” (options - Much better=2, Better=1, Same=0)					
• Able to understand your illness					
• Able to cope with your illness					
• Able to keep yourself healthy					
• Able to cope with life					
• Confident about your health					
• Able to help yourself					
Reference values: In a GP sample patient mean PEI score was 4 points (1 wk later)					
MSK-HQ score – Mean (SD)					
Reference score at Follow-up:					
• Mean MSK-HQ in National FCP pilot = 41					
• Mean MSK-HQ in Community physio = 42					
• Mean MSK-HQ in GP sample = 37					
• Mean MSK-HQ in Ortho hip and knee post-surgery = 42					
MSK-HQ BL to 2Wk change score – Mean (SD)					
Percentage of patients who achieved MCID (>= 6 points)					
The Consumer Health Activation Index (CHAI) score – Mean (SD) ^a					
There is no reference value yet for this score					
Low (CHAI score 0-79)					
Moderate (CHAI score 80-94)					
High (CHAI score 95-100)					
The Consumer Health Activation Index (CHAI) BL-2W change score – Mean (SD)					
Percentage of patients who moved to an improved CHAI category					
Valuing Patients as Individuals Scale – Care and respect [scores range from 5 to 15: higher is better valued] The item asks if patients felt:					
- The clinic staff listened attentively to what they said					
- The clinic staff were very approachable and easy to talk to					
- The clinic staff treated me kindly					
There are no reference values yet, but this score is high					
Valuing Patients as Individuals – Understanding & engagement [scores range from 5 to 15: higher is better valued] The item asks if patients felt:					
- My problems were regarded as important by the therapist					
- The therapist answered all my questions					
- The therapist treated me as an intelligent human being					
There are no reference values yet, but this score is high					

Patient reported experience measures at 2 weeks

Patient reported experience measures at 2 weeks					
Friends and Family Test:					
How likely are you to recommend this service to friends and family if they need similar care or treatment?					
Extremely likely					
Likely					
Neither likely nor unlikely					
Unlikely					
Extremely unlikely					
Don't know					
Was it easy for you to get to the clinic?					
Very easy					
Easy					
Uncertain					
Not easy					
Not easy at all					

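### The SAP lets unblinded analysts transform the primary PEI score after an unspecified normality check, although the raw-scale t-test it is powered on needs no rescue

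*SAP*

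**What the plan says.** SAP section 5 sizes the study for a "two-sample t-test with a two tailed 5% significance level at 80% power" and says "the study is powered to find a 0.40 effect size". With the SD of 3.86, it adds that "the implied MCID between the groups would be a score of 1.55 scale points" and that "the required sample is 100 in each arm". The PEI has six three-point items and is scored 0 to 12.

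SAP section 7 makes an independent-samples t-test on mean PEI the primary analysis, reported as a mean difference with a 95% CI and a standardised effect. It then adds a residual check: "if deviation is found appropriate transformations will be made to the PEI score". The section gives no test or threshold for deviation, no named transformation, no back-transformation and no fallback if the transformed score also fails. It does not say whether the raw or the transformed result is primary. Under the technical details, the two study statisticians analyse the primary outcome unblinded.

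The missing-data sensitivity analysis in the same section is in raw points: "Analyses will be done with missing values both ± 1.55 scale points (the implied MCID) on the PEI". The SAP section 9 shells ask for PEI as mean (SD), with a mean (95% CI) column. Protocol section 8.3 plans mean differences with 95% CIs and mentions no transformation.

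**The concern.** A score with 13 possible values, a floor at 0 and an SD of 3.86 is unlikely to look normal to any formal test at this sample size. If the rule is applied that way, the primary analysis moves off the PEI scale. A difference in mean root-PEI or log-PEI answers a different question from a difference in mean PEI and has no fixed equivalent of 1.55 points.

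Because nothing is named, three decisions would be made after the data are seen, by people who know which phase is which: whether deviation was found, which transformation is appropriate, and which result leads. This affects the only outcome for which the study has a power calculation.

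**Working it through.** **Inputs from the documents.** Two-sided 5%, 80% power, effect size 0.40, 100 per phase (SAP section 5); range 0 to 12 (SAP section 5); SD, "The expected SD for the population is 3.86" (Protocol section 8.1, same figure in the SAP); items scored 2, 1 or 0 (SAP section 9). The only PEI mean given is a reference value in the SAP section 9 shells: "In a GP sample patient mean PEI score was 4 points (1 wk later").

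**Assumptions.** The documents give no expected control mean for this clinic and no distribution. I take control means of 4 to 6, three shapes on 0 to 12 (beta-binomial, rounded and censored normal, discrete exponential-quadratic), and SD 3.86 with 3.0 as a sensitivity value. The planned shift is 0.40 SD.

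**1. The plan's own figure.** 0.40 × 3.86 = 1.544 points (the SAP gives 1.55). Per phase, n = 2 × (1.960 + 0.842)² / 0.40² = 98.1, so 99. The exact t calculation gives 99.1, so 100. Power at 100 per phase is 80.4%. The stated figure is reproduced.

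**2. Would a formal check trigger the rule?** At mean 4, zero lies 4 / 3.86 = 1.04 SD below the mean. A normal curve would put Φ(−1.04) ≈ 15% below 0 and about 2% above 12. At mean 6 it would put 2 × Φ(−6/3.86) ≈ 12% outside the scale. Under the assumed shapes, 22% to 31% of control scores are exactly 0 at mean 4. Shapiro-Wilk at 5% on within-phase residuals, 100 per phase, rejected:

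- SD 3.86, means 4 to 6: 100% of trials
- SD 3.0: 90% to 100%

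**3. Would transforming cure it?** At SD 3.86, after square root, log(x+1), Box-Cox, arcsine or logit, the test still rejected in 99.7% to 100% of trials. At SD 3.0 it rejected in 65% to 100%, depending on the transformation. A monotone transformation can move a lump of zeros but cannot spread it.

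**4. Is a cure needed?** Raw t-test at SD 3.86, 100 per phase: type I error 3.8% to 6.1% (Monte Carlo error about ±1.4 points), power 78% to 82% at the planned shift.

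**5. What transforming does to power at the planned shift (SD 3.86).**

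| Control mean | Raw | Square root or log(x+1) |
|---|---|---|
| 4 | about 80% | about 85% to 89% |
| 6 | about 80% | about 66% to 75% |

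**6. Equal means, unequal spread.** Illustrative beta-binomial case, mean 4 in both phases, SD 3.86 in one. Rejection rates:

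| Other phase's SD | Raw | Square root or log(x+1) |
|---|---|---|
| 3.5 | about 5% | about 7% to 8% |
| 2.5 | about 5% | about 41% to 50% |

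In the last column the transformed tests are picking up a change in spread while mean PEI has not moved.

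**The case against.** The sponsor can make several fair replies.

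- *The rule may never fire.* A reader might infer that any normality check must fail. The SAP names no formal test, and residuals could be judged from plots. This stands: near-certainty applies only to a formal test such as Shapiro-Wilk. It does not rescue the rule, because the leniency of a visual check would be decided unblinded.
- *Strong skew is not established.* The mean of 4 is a GP-sample reference, not a planning value for this clinic. Under the beta-binomial, skewness is 0.65 at mean 4 with 26% zeros, 0.30 at mean 5 with 15%, and 0 at mean 6 with 9%. This stands, but the formal test rejects at all three means.
- *Transforming is neither invalid nor always costly.* With identical distributions in both phases the transformed tests hold close to 5%, and at a control mean of 4 they gain power. This also stands. The difficulty is a changed target quantity with power that moves either way.
- *The unequal-spread case is hypothetical.* Nothing in the documents predicts a fall in SD to 2.5, and at 3.5 the effect is small. The transformed test is then detecting a real difference in distribution, but not one in mean PEI.
- *The ±1.55 analysis need not break.* The shift can be applied to imputed raw scores, truncated to 0 to 12, before any transformation. Agreed.
- *Raw reporting is retained.* The mean difference and the table columns remain in the SAP, which never says that a transformed result replaces them. True; but it does not say which of the two decides the primary hypothesis.

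**Conclusion.** The concern holds as a should-fix. The SAP's transformation rule leaves the primary quantity and p-value open until unblinded analysts have seen the data. Under a formal test it would almost always be invoked (100% of simulated trials at SD 3.86, 90% to 100% at SD 3.0) and would usually not achieve its aim. It is also unnecessary, since the raw t-test at 100 per phase keeps about 5% type I error and 78% to 82% power. If used, it would move power at the planned shift to somewhere between about 66% and 89%, depending on a control mean that nobody knows yet.

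These figures rest on the documents' SD, range and sample size, and on assumed means and shapes. The documents do not support the stronger conclusions that the rule is bound to fire, that the PEI must be strongly skewed, that transformed tests are invalid, or that the missing-data analysis cannot be carried out.

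**What to change.** In SAP section 7, delete the transformation sentence. State instead that the primary result is the difference in mean PEI points between phases with a 95% CI from a Welch t-test, whatever the shape of the residuals. Name one supportive check in advance, such as a bootstrap CI for the mean difference, and say that it does not replace the primary result. Residual plots may still be reported as description.

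This keeps the SAP's t-test framework; the SAP plans no regression for the primary outcome and none is needed for this repair. The result stays comparable with the 1.55-point target, the ±1.55 sensitivity analysis and the table shells. The cost is one SAP sentence and a small extra analysis, with no added data collection or patient burden.

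### Only the primary enablement score is imputed and stress-tested; patient-survey secondary outcomes, including all 3-month scores, get observed-case t-tests with no missing-data check

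*SAP*

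**What the plan says.** **Primary outcome.** SAP section 7 plans to explore patterns of missingness against baseline. It then says that under a missing-at-random (MAR) assumption "missing data on the primary outcome measure will be imputed via the multiple imputation by chained equation (MICE) method". A sensitivity analysis shifts the missing PEI values by 1.55 points in either direction.

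**Secondary outcomes.** The same section analyses these by t-test, with effect sizes, 95% confidence intervals, p-values and a 5% rejection rule. It adds: "No sensitivity analyses will be undertaken and no corrections for multiplicity will be made for the secondary outcomes". Neither document gives a missing-data method for them. Protocol section 8.3 allows adjustment for differences between phases where appropriate, but does not mention missing data.

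**Expected loss.** Protocol section 8.1: "If we account for 50% dropout and missingness, the target recruitment is 200 in both phases 1 and 3". SAP section 5 has the same 100 evaluable per phase but allows 20% and recruits 120. Both allowances belong to the 2-week PEI calculation. No figure is given for 3 months.

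**Measurement times (protocol Table 1).**
- MSK-HQ and CHAI: baseline, 2 weeks and 3 months.
- WPAI: baseline and 3 months.
- PEI and global change: 2 weeks and 3 months.
- Valuing Patients: 2 weeks only.

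**The concern.** The SAP accepts that a responders-only analysis is not enough for the 2-week PEI. MSK-HQ, CHAI and global change come from the same survey and are lost with the same non-returners, yet they get neither imputation nor a sensitivity analysis. The 3-month scores lose more patients still.

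The comparison is non-randomised, and the intervention could change who returns. Under protocol section 4.1, Phase 3 patients re-take the MSK-HQ and can then view progress charts; Phase 1 runs without the Tracker components. If the charts hold on to patients who are doing better, a phase difference can appear with no effect behind it.

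The results will be used. Protocol section 8.3 reads effect sizes across clinical outcomes to decide where the Tracker had an impact. Primary and secondary results would also describe different groups: all recruits for the imputed PEI, responders for the rest.

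**Working it through.** **1. The plan's own figures.** Inputs: "independent groups two-sample t-test with a two tailed 5% significance level at 80% power"; "the study is powered to find a 0.40 effect size"; "The expected SD for the population is 3.86".
- Difference: 0.40 × 3.86 = 1.544, which the plan gives as 1.55.
- n per phase = 2 × (1.96 + 0.84)² / 0.40² ≈ 98.1, so 99. The exact t-test solution is 99.1, so 100, as stated.
- Protocol: 100 / (1 − 0.5) = 200, which reproduces.
- SAP: 120 × 0.8 = 96 observed. (100 / (1 − 0.2) would be 125; that is a separate matter.)

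About 100 (protocol) or 96 (SAP) patients per phase would therefore supply 2-week data.

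**2. What the planned check does for the PEI.** Shifting missing values by 1.55 in one phase moves that phase's mean by (fraction missing) × 1.55: 0.5 × 1.55 = 0.78 points, or 0.2 × 1.55 = 0.31 points. No secondary outcome has an equivalent.

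**3. Bias by formula.** Bias in a phase mean = (fraction missing) × (responder mean − non-responder mean). The documents give no gap, so assume 0.2 to 0.5 SD in one phase only. For m observed per phase and bias b, the SE is √(2/m), and the rejection probability under no effect is 1 − Φ(1.96 − b/SE) + Φ(−1.96 − b/SE).

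| Loss | m per phase | Bias (SD) | Rejection |
|---|---|---|---|
| 50% | 100 | 0.10 to 0.25 | 11% to 42% |
| 20% | 96 | 0.04 to 0.10 | 6% to 11% |

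**4. Simulation carried to 3 months.** All of these are assumptions:
- no true effect;
- correlations of 0.6 to 0.75 between time points;
- 2-week response depends on the baseline score;
- 80% of 2-week responders return at 3 months, depending on the 2-week score;
- log-odds slope 0.3, 0.5 or 0.7 per SD in Phase 3 and zero in Phase 1;
- equal response rates in the two phases.

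Observed at 3 months: 200 × 0.5 × 0.8 = 80, or 120 × 0.8 × 0.8 ≈ 77 per phase.

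| 2-week loss | 3-month bias (SD), slopes 0.3 / 0.5 / 0.7 | False positives |
|---|---|---|
| 50%, 200 per phase | 0.13 / 0.20 / 0.28 | 13% / 25% / 43% |
| 20%, 120 per phase | 0.08 / 0.12 / 0.17 | 8% / 12% / 18% |

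At 2 weeks the effect is smaller. It is about 0.09 to 0.22 SD (10% to 36%) at 50% loss and about 0.04 to 0.10 SD (5% to 10%) at 20%.

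For scale, if the 3-month PEI also has SD 3.86, the 3-month bias is 0.08 × 3.86 = 0.31 to 0.17 × 3.86 = 0.66 points at the SAP's loss. At the protocol's loss it is 0.13 × 3.86 = 0.50 to 0.28 × 3.86 = 1.08 points. The target difference is 1.55.

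**5. Benign cases.** With zero slope in both phases, rejection is about 5%. With the same non-zero slope in both phases, bias is about zero and rejection is 4% to 6%.

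**The case against.** **The asymmetry is assumed.** Both phases use the same platform, online consent and survey schedule. Nothing in the documents shows that response depends on score in one phase and not the other. This stands: the figures describe a risk, not an expected result.

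**The 50% is the less favourable of two conflicting figures.** The SAP, which contains the rule at issue, plans on 20%. This stands too, so both are shown. The effect shrinks at 20% but does not vanish at 3 months.

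**The scope is limited.** A reader might infer that every secondary outcome is affected. The documents do not support that. Clinician behaviours come from the case report form, not from survey return. The 3-month PEI could arguably be read as covered by the primary-outcome rule, although SAP section 5 fixes the primary outcome at 2 weeks. For Valuing Patients, if baseline scores predict it at only 0.2 to 0.3 (an assumption), the bias at 50% loss is 0.03 to 0.09 SD and rejection 5% to 9%. With no baseline and no second measurement, imputation can do little for it.

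**Imputation is not a cure.** A reader might infer that MAR imputation would remove the bias. In a simulation it does (below 0.01 SD), but only because the missingness was generated from the variables in the imputation model. It gives no protection if response depends on the unseen score.

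**Some visibility already exists.** The SAP explores missingness against baseline, and its section 9 tables show survey completion and reminders by phase. Readers would see unequal return, but the secondary estimates would not change. Protocol section 8.3 reserves formal hypothesis testing for enablement; the SAP nonetheless sets a 5% rejection rule for secondary outcomes.

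**Conclusion.** The gap is in the text: imputation and the shift check stop at the PEI, and sensitivity analyses for secondary outcomes are ruled out. Observed-case analysis is an inference, since the SAP does not use the term, but it is the natural reading of a t-test with no stated imputation.

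The practical weight falls on the 3-month scores. The ranges in the second table rest on the assumed slopes, correlations and 80% retention, and on response depending on score in Phase 3 only. The documents do not support saying that the secondary results will be biased, or that the false-positive rate will be near its upper figure. Nor is the lack of multiplicity correction at issue here. The primary result is untouched.

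This is a cheap improvement worth making before analysis, at the level of consider to should.

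**What to change.** Amend SAP section 7 as follows.

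1. Extend the planned MICE model, run within phase, to MSK-HQ and CHAI at 2 weeks and 3 months and to PEI at 3 months. Include WPAI and global change where predictors exist. Use baseline MSK-HQ, baseline CHAI and the outcome's other time point as predictors.
2. Derive the percentage reaching the 6-point MSK-HQ threshold from the imputed data.
3. Print observed-case results and the number observed by phase beside each imputed estimate.
4. Add a delta-shift check for MSK-HQ and CHAI. The 6-point MSK-HQ threshold is a natural shift: it moves a phase mean by 0.2 × 6 = 1.2 points at 20% missing and 0.5 × 6 = 3.0 at 50%. The documents give no such threshold for CHAI; the PEI shift equals 1.55 / 3.86 = 0.40 SD, and the same multiple could serve.
5. Leave Valuing Patients and the categorical experience items as observed-case, with numbers observed and a note that they describe responders only.

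The cost is SAP wording, modest programming on a procedure already planned, longer tables and reliance on MAR for the main secondary estimates. It needs no new data and no change in sample size.

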4 STUDY DESIGN

The study is using a 'before' and 'after' sequential comparison design with an iterative pilot and user testing phase in between. In addition, audio recordings of the consultation (in a sub-sample, n=40 (phase 1=20 & phase 3=20)), alongside individual clinician and patient interviews and a feedback workshop with clinicians and patients, will explore the feasibility, and impact of implementing the MSK-Tracker within routine consultations and the experiences of those who have used it.

Phase 1 ('Before' stage). Patients (approx. n=200) who meet the eligibility criteria for having long-term MSK pain and an appointment at participating clinical sites, will be consented and recruited to complete the e-PROM survey and demographic information shortly before their consultation. This phase will seek to collect patient information via the online digital health platform without using the new innovative 'MSK-Tracker' components, in order to give a baseline of what changes are observed before the MSK-Tracker intervention is used. Patients will complete data online before clinic, and then 2 weeks and 3 months after clinic and their change scores examined. Clinicians will complete a case report form (CRF) using the clinician portal to record clinical behaviours within the consultation. Audio recordings of approximately 20 patient consultations will examine consultation conversations and their content.

Phase 2. ('Pilot stage'). The MSK-Tracker will be developed and optimised through an iterative user testing framework with patients, clinicians, software provider, and experts. The MSK-Tracker will have a number of key 'care planning' components including, pre-clinic preparation, clinic dashboard, summary action plan, personal goal setting and follow-up and progress charts.

Early pilot testing of the MSK-Tracker will mirror the processes used in phase 3, with a limited number of patients and clinicians using the Tracker. We will aim to recruit approximately 40 patients (in up to 2 cycles of 20) to use the MSK-Tracker. During this phase we will invite all patients and clinicians to take part in an interview about their experiences to identify further potential improvements that can be

made to the Tracker before commencing phase 3. We aim to interview up to 10 patients in each of up to 2 cycles.

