4.1 Interventions/Treatments

The intervention is not a treatment per se, but involves patients and clinicians engaging with the MSK-Tracker software. It is envisaged that the MSK-Tracker will facilitate a new care planning approach with the following distinct components:

- **Pre-clinic preparation.** Prior to a consultation, the MSK-Tracker will help patients to set their clinic agenda by asking them to think about the ways in which their long-term MSK condition is impacting on their lives.
- **Clinic dashboard.** During the consultation it will enable the clinician to see the patient's health impact from their MSK condition (using MSK-HQ), and present the patient's clinic agenda to inform the consultation focus and ensure the individual's specific needs are addressed.
- **Summary action plan.** The Tracker will be used to record the agreed action plan from the consultation, including advice, information, referrals and investigations, which the patient can access when they want to as a reminder of what was agreed.
- **Personal goal setting.** To help the patient focus on what they personally seek to change (e.g. to get more fit and active) in relation to the impact of the MSK condition on their life and to help them reflect on what things are helping/hindering them to achieve goals to reduce this impact a goal setting module will be available to patients within the Tracker.
- **Follow-up and monitoring.** The Tracker will enable the patient to re-take the MSK-HQ at 2 weeks and 3 months and then have the opportunity to look at tracker charts that show their progress on the MSK-HQ overall score and individual domains.

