7.4 Follow up data at 2 weeks

Patients will complete an assessment using the e-PROM/MSK-Tracker 2 weeks after their clinic appointment. See Table 1 (page 20) for details of the assessment questions.

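### The SAP's only missing-not-at-random check on the PEI does not say how the ±1.55 shift applies by phase; a shift common to both phases cannot show non-response that differs between them

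*SAP*

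**What the plan says.** The primary result is a difference in mean PEI at 2 weeks between phase 1 and phase 3, tested by a two-sample t-test (SAP section 7, Primary outcome measure). Missing PEI values are imputed by MICE under MAR, after missingness has been explored against baseline. One sensitivity analysis follows: "Analyses will be done with missing values both ± 1.55 scale points (the implied MCID) on the PEI". Its stated purpose is "to model the potential effect of Missing Not at Random Bias", and shifted values are held within 0-12. The word 'both' refers to the two signs; nothing says whether the shift falls on phase 1, phase 3, each in turn, or all missing values together. The SAP plans no other missing-not-at-random (MNAR) check, and Protocol 8.3 plans none.

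Related text:
- SAP section 6 accepts that "patient groups are not randomly allocated".
- The feasibility table in SAP section 9 has a row by phase for "Patient completed 2-week FU survey".
- Protocol section 4, on phase 1: "This phase will seek to collect patient information via the online digital health platform without using the new innovative" Tracker components.
- Protocol 4.1, among the Tracker's components: "The Tracker will enable the patient to re-take the MSK-HQ at 2 weeks and 3 months".
- Protocol 7.4, without distinction by phase: "Patients will complete an assessment using the e-PROM/MSK-Tracker 2 weeks after their clinic appointment".
- On missingness, SAP section 5 states: "If we account for 20% dropout and missingness, the target recruitment is 120 in both phases 1 and 3". Protocol 8.1 allows 50% and recruits 200 per phase.

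**The concern.** A check on MAR is useful for this comparison only if it can move the phase difference in the way a plausible bias would. Raising or lowering every missing value by the same amount moves both phase means together, so most of the shift cancels. Such a check is valid for non-response that is alike in the two phases, and it has some force when response rates differ. It does not represent non-responders who fall below their MAR prediction in one phase but not in the other.

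There is reason to consider that case. The cohorts are recruited one after the other without randomisation. Of the two phases compared, only phase 3 uses the Tracker, so replying at 2 weeks could be tied to engagement with the intervention, and enablement could be too. Counting completion by phase and relating missingness to baseline show differences in rate and in measured predictors, not in the unobserved scores.

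At stake is a primary result reported as robust to MNAR when the check could hardly have shown otherwise.

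**Working it through.** **1. The plan's own figure.** Inputs from SAP section 5: effect size 0.40, SD 3.86, two-sided 5%, 80% power. 0.40 × 3.86 = 1.544, stated as 1.55. The t-test sample size is 99.08 per phase, so the stated 100 reproduces.

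**2. What a shift does.** If a fraction m of a phase is missing and each imputed value moves by d, that phase's mean moves by m × d. So, before truncation:

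change in (phase 3 − phase 1) = m3·d3 − m1·d1.

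- Common shift, d1 = d3 = ±1.55: ±1.55 × (m3 − m1). This is 0 at equal missingness and 0.155 for a 10-point gap (40% against 50%).
- One phase only: 0.2 × 1.55 = 0.31 at 20% missing; 0.5 × 1.55 = 0.775 at 50%.
- Opposite shifts: 0.62 at 20%; 1.55 at 50%, the whole implied MCID.

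Under truncation, figures for unequal missingness depend on the two base rates and not only on the gap, so none are given here.

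**3. Allowing for truncation to 0-12.** Assumptions: beta-binomial scores with SD 3.86; phase 1 mean 4 (the GP reference value in SAP section 9, assumed to apply here); phase 3 mean 4 + 1.55 = 5.55; imputed values with the same mean as responders in their phase. The nominal shift then has these mean effects:

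| Nominal shift | Phase 1 | Phase 3 |
|---|---|---|
| +1.55 | +1.457 | +1.400 |
| −1.55 | −1.081 | −1.326 |

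**4. Effect on the test.** SE = 3.86 × √(2/100) = 0.546, held fixed at 100 responders per phase. An observed difference of 1.55 gives z = 1.55/0.546 = 2.84. With equal missingness, z = (1.55 + change)/0.546:

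| Scenario | Change, 20% missing | z | Change, 50% missing | z |
|---|---|---|---|---|
| Common, −1.55 (larger effect of the two signs) | −0.05 | 2.75 | −0.12 | 2.61 |
| Phase 3 alone, −1.55 | −0.27 | 2.35 | −0.66 | 1.62 |
| Phase 1 alone, +1.55 | −0.29 | 2.31 | −0.73 | 1.50 |
| Phase 1 +1.55 and phase 3 −1.55 | −0.56 | 1.82 | −1.39 | 0.29 |

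The 20% and 50% rates serve only as a range taken from the two documents.

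**5. How far this depends on the assumptions.**
- Phase 1 mean from 3 to 5, phase 3 mean 1.55 higher: common shift z at least 2.49; phase 3 alone 2.32 to 2.40 at 20% and 1.55 to 1.75 at 50%; phase 1 alone 2.30 to 2.32 and 1.50 to 1.53; opposite 1.80 to 1.87 and 0.24 to 0.41.
- With 96 responders (80% of 120), SE is 0.557 and each z falls by about 2%.
- The observed difference matters most. Significance needs a difference of 1.96 × 0.546 = 1.070. For a phase 3 shift alone, with its mean effect held at 1.326, the missing rate at which significance is lost is (1.2 − 1.070)/1.326 ≈ 10% for an observed 1.2, (1.55 − 1.070)/1.326 ≈ 36% for 1.55, and (2.0 − 1.070)/1.326 ≈ 70% for 2.0.

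**The case against.** **The text is ambiguous, not wrong.** A reader might infer that the SAP prescribes a common shift. It does not; phase-specific use is open. What stands is that the wording does not require it, and someone following it literally would apply one shift to everything.

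**The mechanism is not in the documents.** A reader might infer that the 2-week PEI survey is itself part of the Tracker, so that phase 3 non-response must reflect engagement with it. The documents do not support this. Protocol 4.1 speaks of re-taking the MSK-HQ, not of the PEI or the survey. Phase 1 patients also complete 2-week data online on the same platform, phase 3 follows the same survey schedule, and Protocol 3.4 describes the email and text reminder without distinction by phase. Phase-specific MNAR is a plausible inference and no more.

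**MICE may already absorb part of it.** The Consumer Health Activation Index (CHAI), MSK-HQ and health literacy are collected at baseline. If they enter the imputation model, non-response that they predict is handled under MAR and only the remainder is MNAR. This is fair, but the SAP does not list the imputation predictors.

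**The effect is modest at the SAP's own rate.** At 20% missing no one-phase shift removes significance in the illustration; only the more extreme opposite shifts do. This also stands. The SAP deserves credit for going beyond MAR with a prespecified, MCID-sized, truncated shift.

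**Conclusion.** The concern holds as a gap in specification with a real consequence. The only MNAR check does not say how the shift applies by phase. On its plain reading, it cannot show the effect of departures from MAR that differ between phases.

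The choice of reading makes little difference to the conclusion at 20% missing. At the protocol's 50% it can reverse it: z at least 2.61 for a common shift at equal missingness, against 1.50 to 1.62 for the same shift in one phase. This rests on an observed difference of 1.55, assumed phase means, imputed means equal to observed means, and a fixed SE that ignores imputation variance.

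A reader might take 36% missing as a general threshold for losing significance. It is not: the figure runs from about 10% to about 70% as the observed difference goes from 1.2 to 2.0. Nor do these figures show that the trial's result would be overturned. They show that the check, read plainly, need not examine the question. It should be changed because the change is cheap, and because the SAP has the primary outcome analysed unblinded, so the choice is better fixed in writing beforehand.

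**What to change.** Add a sentence to SAP section 7: the ±1.55 shifts are applied to the MICE output by phase (phase 1 alone, phase 3 alone, and opposite directions in the two phases), alongside the common shift, with truncation to 0-12 kept. Optionally, report the phase 3 shift at which the 95% confidence interval first includes zero; in the illustration with an observed difference of 1.55 it is about −3.0 points at 20% missing and −1.1 at 50%.

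The cost is one sentence and a short loop over imputations that will already exist. The downside is slightly more analysis to report and a result that may look less robust. If phase-specific shifts were always intended, the edit only records that.
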